2.4.3 Extent of investigational medicinal product exposure and compliance

The extent of IMP exposure and compliance will be assessed and summarized by actual treatment within the safety population ([Section 2.3.2](#)).

2.4.3.1 Extent of investigational medicinal product exposure

The extent of IMP exposure will be assessed by the duration of IMP exposure.

Duration of IMP exposure is defined as last dose date of IMP – first dose date of IMP + 1 day, regardless of unplanned intermittent discontinuations (see [Section 2.5.3](#) for calculation in case of missing or incomplete data).

Duration of IMP exposure will be summarized descriptively as a quantitative variable (number of patients exposed, mean, SD, median, minimum, and maximum). In addition, duration of treatment exposure will also be summarized categorically by numbers and percentages for each of the following categories and cumulatively according to these categories:

- 1 to 28 days,
- 29 to 56 days,
- 57 to 84 days,
- 85 to 126 days,
- 127 to 168 days
- 169 to 175 days
- 176 to 182 days
- >182 days

Additionally, the cumulative duration of treatment exposure will be provided, defined as the sum of the duration of treatment exposure for all patients, and will be expressed in patient years.

Number and percentages of patients by final dose at the end of the treatment will also be presented by each treatment group.

2.4.3.2 Compliance

A given administration will be considered noncompliant if the patient did not take the planned dose of treatment as required by the protocol. No imputation will be made for patients with missing or incomplete data.

Percentage of compliance for a patient will be defined as the number of days that the patient was compliant divided by the total number of days that the patient was planned to take during the treatment period from the first date to the last date of IMP administration.

$$\text{Compliance rate (\%)} = \left[\frac{\text{Total number of days with IMP injection}}{\text{Planned number of days with IMP injection}} \right] \times 100$$

Above-planned dosing percentage for a patient will be defined as the number of days that the patient took a higher dose than planned divided by the total number of days that the patient was planned to take during the treatment period.

Under-planned dosing percentage for a patient will be defined as the number of days that the patient took a lower dose than planned divided by the total number of days that the patient was planned to take during the treatment period.

Treatment compliance, above-planned, and under-planned dosing percentages will be summarized descriptively as quantitative variables (number, mean, SD, median, minimum, and maximum). In addition, the percentage of patients who have <60%, ≥60 to <80%, ≥80 to ≤100%, and >100% compliance will be summarized by treatment group.

Cases of overdose (see study protocol for further details) will constitute AEs/SAEs and be analyzed as such.

2.4.4 Analyses of efficacy endpoints

Efficacy analyses will be performed on the ITT population using the efficacy assessments collected during the study, including those obtained after IMP discontinuation or introduction of rescue therapy, unless otherwise specified.

The primary efficacy endpoint will only be summarized by descriptive statistics without formal statistical testing due to limited sample size and insufficient power.

Missing data for efficacy analyses is identified through steps described in [Section 2.5.3](#).

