1.2 OBJECTIVES

1.2.1 Primary objectives

- To demonstrate the superiority of Soliqua 100/33 versus Lantus in the HbA1c change from baseline to Week 26 within the overall population.
- To demonstrate the benefit of Soliqua 100/33 versus Lantus in the HbA1c change from baseline to Week 26 within each ethnic/racial subgroup evaluated (i.e., Hispanics of any race, non-Hispanic black/African Americans and non-Hispanic Asians).

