1.4 STUDY PLAN

R = Randomization; patients will continue their background OADs at stable doses throughout the study; background basal insulin will be stopped and replaced with the IMP.

a: Stratified by (1) ethnicity/race, (2) HbA1c at visit 1, (3) background use of SGLT2 inhibitors and (4) background SU use.

b: A sub-set of patients only.

= Remote visit (telephone or videoconference) for all sites = On-site (in person) visit for brick-and-mortar sites/ remote visit (telephone or videoconference) for fully-remote sites

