2.4.4.1 Analysis of primary efficacy endpoint(s)

Summaries of the primary efficacy endpoint (change from baseline to Week 26 in HbA1c) will be performed using observed cases for each treatment group based on the ITT population, using HbA1c values obtained during the 26-week randomized treatment period, including those obtained after IMP discontinuation or rescue medication use. The summary will include the number of observations, mean, SD, standard error (SE), minimum, median, and maximum.

Summary statistics at scheduled visits

Summary statistics (for screening value, baseline value, observed post-baseline value and its changes from baseline) at scheduled visits (using observed cases) will be provided for each

treatment group, both for the overall population and separately for each ethnicity/race subgroup. The summary will include the number of observations, mean, SD, SE, minimum, median, and maximum. Graphical presentations will also be used to examine trends over time using mean values (\pm SE) and mean changes from baseline (\pm SE) at each of the scheduled visits.

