2.4.4.3 Multiplicity issues

Not applicable since no formal testing will be performed.

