2.5.5 Pooling of centers for statistical analyses

Center or pooling of centers is not planned and will not be included in the statistical models for efficacy analyses.

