Appendix B Summary of statistical analyses

EFFICACY ANALYSIS

Endpoint	Analysis population	Primary analysis	Supportive analysis	Subgroup analysis	Other analyses
Primary endpoint					
HbA1c: Change from baseline at Week 26, (Soliqua 100/33 vs. Lantus)	ITT	Summary statistics only			Summary statistics for observed values and changes from baseline by visit. Graphical presentations for mean changes from baseline (\pm SE) and mean values (\pm SE) by visit.
Secondary endpoints					
Proportion of patients with HbA1c target of <7% at Week 26; 2-hour PPG, daily insulin glargine dose and body weight: Change from Baseline to Week 26;	ITT				Summary statistics for observed values and changes from baseline by visit. Graphical presentations for mean changes from baseline (\pm SE) and mean values (\pm SE) by visit.
		Summary statistics only			
Other endpoints					
HbA1c change from baseline to Week 12;	ITT	Summary statistics only		No	Summary statistics for observed values and changes from baseline by visit. . For patients requiring rescue treatment: KM plot; List of patients rescued
Proportion of patients requiring rescue treatment by Week 26	ITT				

SAFETY ANALYSES

Endpoint	Analysis Population	Primary analysis	Supportive Analysis	Subgroup analysis	Other analyses
Hypoglycemia	Safety	Follow safety guidelines Number (%) of patients with any hypoglycemia, severe hypoglycemia, documented hypoglycemia, pseudo hypoglycemia and probable symptomatic hypoglycemia during TEAE period, and summary of frequency and incidence rates in 100 patient-years.	No	No	KM plot time to first event of severe hypoglycemia or documented hypoglycemia
Adverse Events	Safety	Follow safety guidelines	No	Common TEAEs by demographic factors including gender (Male, Female), age group (<50, ≥50 to <65, ≥65 years of age), race (White, Black or African American, Asian, other)	No
Clinical laboratory data	Safety	Follow safety guidelines	Descriptive	No	No
Vital signs	Safety	Follow safety guidelines	Descriptive	No	No

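### The primary objectives still promise a comparison of Soliqua with Lantus, but the plan produces only per-arm HbA1c summaries, with no difference, interval or adjustment

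*SAP*

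**What the plan says.** SAP section 1.2.1 gives two primary objectives, both comparative:

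- The first covers the trial as a whole: "To demonstrate the superiority of Soliqua 100/33 versus Lantus in the HbA1c change from baseline to Week 26 within the overall population".
- The second repeats the comparison separately for the three groups: "To demonstrate the benefit of Soliqua 100/33 versus Lantus in the HbA1c change from baseline to Week 26 within each ethnic/racial subgroup evaluated".

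Section 1.3 reports that recruitment difficulty ended the trial early at 240 patients, 120 per treatment, with descriptive evaluation. Section 2.4.4 applies this to the primary endpoint: "The primary efficacy endpoint will only be summarized by descriptive statistics without formal statistical testing due to limited sample size and insufficient power". Section 2.4.4.1 specifies observed-case summaries for each treatment group: "The summary will include the number of observations, mean, SD, standard error (SE), minimum, median, and maximum". The by-visit version is repeated within each ethnicity/race group, with plots of arm means ± SE. On multiplicity, section 2.4.4.3 says "Not applicable since no formal testing will be performed".

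Two other places still read as if a comparison were planned. Appendix B names the primary endpoint as "HbA1c: Change from baseline at Week 26, (Soliqua 100/33 vs. Lantus" but lists nothing beyond summary statistics for it. Section 2.5.5 says "Center or pooling of centers is not planned and will not be included in the statistical models for efficacy analyses", although section 2.4.4 contains no model.

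Randomisation used four factors, given in section 1.4: "Stratified by (1) ethnicity/race, (2) HbA1c at visit 1, (3) background use of SGLT2 inhibitors and (4) background SU use".

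**The concern.** Both objectives are about a difference between arms, and no planned efficacy output estimates one. The table in section 1.6 records that early termination changed the sample size and the efficacy analyses. The objectives were not changed with them, so sections 1.2.1 and 2.4.4 now disagree about what the trial is to deliver.

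The reason given for the descriptive approach is lack of power. That supports dropping a confirmatory test. It does not support dropping the estimated difference and its interval, because the interval is how limited precision is shown.

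As planned, a reader must subtract two arm means and build an unadjusted interval by hand from the per-arm SEs. An adjusted interval cannot be recovered from those summaries at all. The ± SE plots are also easy to misread as a comparison. The main limitation after early termination, wide uncertainty within each ethnic/racial group, is never displayed for the difference.

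**Working it through.** **What is planned, objective by objective**

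| Objective (1.2.1) | Quantity needed | Planned output (2.4.4, 2.4.4.1, Appendix B) |
|---|---|---|
| Superiority, overall | Difference in HbA1c change with its uncertainty | n, mean, SD, SE, minimum, median, maximum per arm |
| Benefit in each group | The same, within each of three groups | The same per-arm summaries by visit |

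The only between-arm estimate with an interval anywhere in the SAP is the relative risk for safety variables in section 2.4.5, and it is optional. Baseline HbA1c and the stratification factors are used for change scores, baseline tables and subgroup display, never for adjustment.

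**Sample size.** Section 1.3 gives no alpha, power, effect size or SD, so there is no power calculation to reproduce. The arithmetic agrees: 2 × 120 = 240.

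**Precision the trial could report**

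Input from the SAP: 120 per arm. Assumed: SD of change 1.0, 1.1 or 1.3 percentage points; three groups of equal size (120/3 = 40 per arm); 15% without a Week 26 value (0.85 × 120 = 102; 0.85 × 40 = 34).

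Half-width of the unadjusted 95% CI = t(0.975, 2n−2) × SD × √(2/n). Example with n = 120 and SD 1.1: 1.970 × 1.1 × √(2/120) = 1.970 × 0.142 = 0.280.

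| n per arm | SD 1.0 | SD 1.1 | SD 1.3 |
|---|---|---|---|
| 120 (overall) | 0.254 | 0.280 | 0.331 |
| 102 (overall, 15% missing) | 0.276 | 0.304 | 0.359 |
| 40 (one group) | 0.445 | 0.490 | 0.579 |
| 34 (one group, 15% missing) | 0.484 | 0.533 | 0.630 |

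**Effect of adjustment.** If baseline HbA1c correlates with change at |r| (assumed 0.3 to 0.5), the residual SD is SD × √(1 − r²). At 120 per arm the half-widths for the three SDs are:

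- r = 0.3: 0.243, 0.267, 0.315
- r = 0.5: 0.220, 0.242, 0.286

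The full main-effects model has eight parameters (intercept, treatment, baseline HbA1c, two for ethnicity/race, and one each for the HbA1c stratum, SGLT-2 inhibitor use and SU use). That leaves 240 − 8 = 232 residual degrees of freedom. Using 234 instead gives the same figures to three decimals.

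**Power, to test the stated reason.** Noncentral t, two-sided 5%, for SD 1.0, 1.1 and 1.3:

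- Overall (120 per arm), difference 0.3: 64%, 56%, 43%
- Overall, difference 0.4: 87%, 80%, 66%
- Overall, difference 0.5: 97%, 94%, 84%
- One group (40 per arm), difference 0.5: 60%, 52%, 40%

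Power within groups is low throughout. Whether it is insufficient overall depends on an effect size and SD that the SAP does not state.

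**The SE plots.** If two arms have equal SE and their bars just touch, the means differ by 2 SE. The SE of the difference is √2 × SE, so z = 2/√2 = 1.41 and two-sided p = 0.16. Bars that separate slightly can look like clear evidence when they are not.

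**The case against.** The strongest reply is that descriptive-only analysis was deliberate, disclosed and repeated in sections 1.3, 1.6, 2.4.4, 2.4.4.3 and Appendix B. On that view the real defect is one of wording, and restating the objectives as descriptive would remove it. This stands in part. The choice is open and the test need not return. But rewording alone would leave the trial's primary question without a planned estimate.

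Second, per-arm n, mean and SE are reported, so the crude difference and its interval can be recovered, and adjustment gains little: at SD 1.1, from 0.280 to 0.267 or 0.242. That is correct for the overall figure. It is still better for the plan to fix the estimate than to leave each reader to construct one.

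Third, four 95% intervals could be read as four tests. If there were no effect in any of three independent groups, at least one interval would exclude zero with probability 1 − 0.95³ = 14%. This is a fair caution, and the output should carry a label saying so.

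Fourth, objectives are normally set by the protocol, which is not at hand, so rewording them in the SAP alone could create a mismatch. An explanatory note in section 1.2.1 would meet that.

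Fifth, the flow chart schedules pre-treatment HbA1c only at Visit 1, so baseline HbA1c and the HbA1c stratum will usually come from the same measurement. Entering both the continuous value and its stratum is ordinary practice. Separately, section 2.5.3 still sends missing data to multiple imputation under section 2.4.4, which describes none; that needs its own correction.

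**Conclusion.** The concern holds and should be fixed. The mismatch between section 1.2.1 and sections 2.4.4 to 2.4.4.3 is plain from the text and depends on no assumed figure. The data remain valid, and the decision not to test is sound. What is missing is any planned estimate of the quantity that both primary objectives name.

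The size of the loss can only be illustrated, because the SAP gives no SD, correlation, missing-data rate or group sizes. On the assumed values, the overall difference could be reported to within about a quarter to a third of a percentage point. Within groups, the uncertainty is around half a point or more.

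**What to change.** - **Section 2.4.4.1:** add the Soliqua-minus-Lantus difference in HbA1c change at Week 26 with a 95% CI, labelled as estimation with no test. Obtain it from one ANCOVA on the observed cases already specified, with treatment, baseline HbA1c, ethnicity/race, screening HbA1c stratum (<8.5% or ≥8.5%), SGLT-2 inhibitor use and SU use as main effects.
- **By group:** report the same estimate within each ethnicity/race group, omitting ethnicity/race from those models. State that these intervals are not adjusted for multiplicity and are not to be read as tests.
- **Missing data:** state that the observed-case estimate assumes Week 26 values are missing at random given the covariates.
- **Appendix B:** add the matching row.
- **Section 1.2.1:** change the aim from demonstrating superiority or benefit to estimating the difference. If the protocol fixes the objectives, add a note that they are the original ones and will not be formally tested. The reference to insufficient power may stay.

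The cost is SAP wording and one standard model run four times, with no new data or patients. The downside is that the group intervals will be wide.

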2.4.4.1 Analysis of primary efficacy endpoint(s)

Summaries of the primary efficacy endpoint (change from baseline to Week 26 in HbA1c) will be performed using observed cases for each treatment group based on the ITT population, using HbA1c values obtained during the 26-week randomized treatment period, including those obtained after IMP discontinuation or rescue medication use. The summary will include the number of observations, mean, SD, standard error (SE), minimum, median, and maximum.

Summary statistics at scheduled visits

Summary statistics (for screening value, baseline value, observed post-baseline value and its changes from baseline) at scheduled visits (using observed cases) will be provided for each

treatment group, both for the overall population and separately for each ethnicity/race subgroup. The summary will include the number of observations, mean, SD, SE, minimum, median, and maximum. Graphical presentations will also be used to examine trends over time using mean values (\pm SE) and mean changes from baseline (\pm SE) at each of the scheduled visits.

2.4.4.2 Analyses of secondary efficacy endpoints

Analyses of the secondary efficacy endpoints will be performed using the ITT population for all patients and, separately, by ethnicity/race subgroup. The originally collected change from baseline to Week 26 in 2-hour glucose excursion will no longer be considered critical and will not be analyzed.

For all continuous secondary endpoints except 2-hour glucose excursion, summary statistics at scheduled visits and the changes from baseline will be provided using observed cases for each treatment group, both for the overall population and separately for each ethnicity/race subgroup. The summary will include the number of observations, mean, SD, SE, minimum, median, and maximum. Graphical presentations will also be used to examine trends over time using mean values (\pm SE) and mean changes from Baseline (\pm SE) at each of the scheduled visits. For percentage (%) of patients achieving the HbA1c target of <7% at scheduled visits, the proportion in each treatment group will be provided. All values at scheduled visits will be used to determine whether a patient is a responder or not, even if they are measured after IMP discontinuation or introduction or rescue therapy. If no assessment is available at scheduled visits, patients will be treated as failures (non-responders).

2.4.4.3 Multiplicity issues

Not applicable since no formal testing will be performed.

2.4.4.4 Additional efficacy analysis

Analyses of other efficacy endpoints will be performed on the ITT population using all assessments obtained during the 26-week randomized treatment period, including those obtained after IMP discontinuation or introduction of rescue therapy. Descriptive statistics will be summarized by treatment group, both for the overall population and separately for each ethnicity/race subgroup.

All other efficacy variables originally collected, except the change from baseline to Week 12 in HbA1c and percentage of patients requiring rescue therapy by Week 26, will no longer be considered critical and will not be analyzed. The analysis of other endpoints (see [Section 2.1.3.3](#)) will be descriptive with no formal testing.

The number (%) of patients who used rescue therapy and a KM curve for the time to first rescue therapy will be provided by treatment group. A list of patients who used rescue therapy will also be provided. Time to rescue will be defined as the number of days from the first administration of IMP until the start date of any rescue medication. Patients who did not take any rescue medication

during the 26-week treatment period will be considered as censored observations. The censoring time will be the last administration date (e-CRF “Treatment Status Library” page), or the end date of the study (e-CRF “Completion of End of Study/Follow-up” page) if the last administration date is not available, or the last contact date if the last administration date and end date of the study are not available.

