1 OVERVIEW AND INVESTIGATIONAL PLAN

1.1 STUDY DESIGN AND RANDOMIZATION

This study is an open-label, 1:1 randomized, active-controlled, 26-week duration, parallel-group, multicenter, US-only, Phase 3b study to compare the efficacy and safety of Soliqua 100/33 with Lantus overall and in ethnically/racially diverse groups with T2DM inadequately controlled on basal insulin and 1 or 2 OAD agents. The patients will be randomized according to their self-reported ethnicity/race (i.e., Hispanics of any race, non-Hispanic black/African Americans and non-Hispanic Asians). Additionally, to ensure a balanced IMP allocation, randomization will be stratified by their screening HbA1c value ($<8.5\%$ versus $\geq 8.5\%$), the background use of SGLT-2 inhibitors (yes/no) and the background use of SUs (yes/no). Patients will participate in 1 of 2 ways, either at a traditional 'brick & mortar' investigational site, or fully remotely through a virtual arrangement.

The study will consist of 3 periods:

- An up to 2-week screening period
- A 26-week open-label randomized treatment period: at the end of the screening period (Week 0, Visit 2) patients will be randomized to receive either Soliqua 100/33 or Lantus
- A 3-day post-treatment safety follow-up period (not required for patients who prematurely and permanently discontinued IMP administration but stayed in the study through Week 26; these patients should continue all study visits except for the follow-up visit).

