2.3.1 Efficacy populations

Efficacy analyses will be based on the ITT population, defined as all randomized patients. Patients will be analyzed for efficacy analyses according to the treatment group to which they are allocated by the IRT according to the randomization schedule at the randomization visit (as randomized), irrespective of the treatment actually received.

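### The time-to-rescue Kaplan-Meier curve censors non-rescued patients at last IMP dose even when they are followed to Week 26, so it does not describe the same thing as the planned count of patients rescued by Week 26

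*SAP*

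**What the plan says.** Section 2.4.4.4 plans two summaries of rescue plus a patient listing: "The number (%) of patients who used rescue therapy and a KM curve for the time to first rescue therapy will be provided by treatment group". The event has no on-IMP restriction: "Time to rescue will be defined as the number of days from the first administration of IMP until the start date of any rescue medication". Section 2.1.3 likewise identifies rescue from the reason ticked on the eCRF medication page, whether or not the patient is still on IMP.

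Patients with no rescue "during the 26-week treatment period will be considered as censored observations". On when they are censored, the plan says "The censoring time will be the last administration date". The end-of-study date is only a fallback, used "if the last administration date is not available, or the last contact date if the last administration date and end date of the study are" also missing. Longer follow-up does not trigger it.

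The opening of the same section sets the scope as ITT with all assessments, "including those obtained after IMP discontinuation or introduction of rescue therapy". Section 1.1 provides for "patients who prematurely and permanently discontinued IMP administration but stayed in the study through Week 26", who continue their visits, and section 2.2 plans a disposition row for patients who attended Week 26 after stopping IMP. The endpoint in section 2.1.3.3 is the percentage requiring rescue by Week 26.

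Section 2.5.3, however, defines the 26-week randomized treatment period as running from first to last IMP administration on or before Visit 19, and says it is used for selected efficacy parameters.

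**The concern.** A Kaplan-Meier risk set must not depend on what happens later. Take two patients who stop IMP on Day 60 and are both followed to Week 26. One is rescued on Day 120, stays at risk to Day 120 and counts as an event. The other is never rescued and leaves the risk set on Day 60, although known to be rescue-free to Week 26. After IMP stops, only patients who will later be rescued remain in the denominator.

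Under this rule the curve can never lie below the correctly censored one. It lies above it as soon as one followed, non-rescued discontinuer is dropped before someone else's rescue. The excess grows with the share stopping IMP, so unequal discontinuation in this open-label trial would pull the two curves apart without any difference in rescue. Rescue by Week 26 is one of only two endpoints in the 'other' category that are still to be analysed.

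**Working it through.** The SAP gives no rescue rate, discontinuation rate or Kaplan-Meier value, so there is no figure to reproduce. Section 1.3 gives 120 patients per arm. Every other input below is an assumption.

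**Rules compared**
- Literal rule (2.4.4.4): any rescue to Week 26 is an event; non-rescued patients are censored at last dose.
- On-IMP rule (2.4.4.4 read with the period in 2.5.3): only rescue on IMP is an event; everyone else is censored at last dose.
- Aligned rule: same events as the literal rule; non-rescued patients are censored at Day 182 or end of follow-up if earlier.

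Kaplan-Meier risk = 1 − Π(1 − d/n), where d is the number of events and n the number at risk at each event time.

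**Example 1.** Of 120 patients, 24 stop IMP on Day 60 and all are followed to Week 26; 6 of the 24 are rescued on Day 120, and 6 others are rescued on IMP on Day 90.
- Count: 12/120 = 10.0%.
- Literal: 18 leave on Day 60, so n = 102 on Day 90 and 96 on Day 120. 1 − (96/102)(90/96) = 11.8%.
- On-IMP: n = 96 on Day 90. 6/96 = 6.3%.
- Aligned: 1 − (114/120)(108/114) = 10.0%, equal to the count.

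**Example 2.** Again 24 stop on Day 60; 4 of them are rescued on Day 120, and 12 others on IMP on Day 100.
- Count: 16/120 = 13.3%.
- Literal: 1 − (88/100)(84/88) = 16.0%.
- On-IMP: 12/96 = 12.5%, below the count.
- Aligned: 13.3%.

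**Example 3.** As example 2, but with no rescue after stopping.
- Count: 12/120 = 10.0%.
- Literal and on-IMP rules coincide: 12/96 = 12.5%, above the count.

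Examples 2 and 3 show that under the on-IMP rule the gap from the count can have either sign.

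**Simulation of the literal rule.** Assumptions: uniform stopping times among those who stop, 26-week on-IMP rescue risk of 5-20%, post-stop rescue hazard 1 or 3 times the on-IMP hazard, and all discontinuers followed to Day 182. Ratio of the Kaplan-Meier value to the true proportion rescued:

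| Stop IMP | Ratio |
|---|---|
| 10% | 1.03-1.05 |
| 20% | 1.07-1.11 |
| 25% | 1.09-1.14 |

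With a true risk of 10% and equal hazards, the curve ends at about 10.5% if 10% stop and about 11.3% if 25% stop. If one arm had each stopping rate, that would be an artificial gap of 0.8 points.

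A separate set of simulated arms of 120 with exponential stopping times agrees (count versus literal curve): 10.1% versus 10.6% with 10% stopping, and 9.9% versus 11.0% with 20% stopping. Under the aligned rule the Week 26 value equalled the count in every scenario, because follow-up was complete.

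**The case against.** The strongest reply is that the curve was meant as an on-treatment display. If 'the 26-week treatment period' in 2.4.4.4 means the period defined in 2.5.3, rescue after the last dose is not an event. Event window and censoring then match, and the risk set no longer depends on the future. A reader might infer that the curve overstates rescue whatever the reading. The documents do not support that: on this reading it can fall below the count, as in example 2. But the reading does not settle the matter either. Section 2.4.4.4 expressly includes data after IMP discontinuation, which would leave the 2.5.3 definition almost nothing to include. The curve would also sit beside a count and an endpoint defined by Week 26 rather than by last dose.

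The second reply concerns importance, and much of it stands. The retained endpoint is reported directly as number (%) with a listing. Appendix B places the curve under other analyses. No test is planned, and section 2.4 makes all analyses conditional on sufficient data. Section 2.1.2 describes rescue as added while study treatment continues, so rescue after stopping may be uncommon, although nothing excludes it. The 0.8-point gap is about one patient in 120, against a standard error of √(0.10 × 0.90/120) = 2.7 points. A Kaplan-Meier value and a crude percentage also differ legitimately when patients are truly lost to follow-up. The objection here is to censoring patients who are still observed.

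A reader might also infer that never-treated ITT patients have no time origin, since "Efficacy analyses will be based on the ITT population, defined as all randomized patients" and the clock starts at first IMP. Section 2.5.3 covers this: Day 1 is the day of randomization if the patient was not exposed. The fallback in 2.4.4.4 gives such patients a censoring date. No change is needed there.

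**Conclusion.** The point holds as a mismatch between event window, censoring rule and count, with an unresolved conflict between 2.4.4.4 and 2.5.3. On the literal wording of 2.4.4.4 the curve is biased upward by about 3-14% in relative terms, roughly 1 point at a 10% risk. That size rests wholly on the assumed stopping and rescue rates and on complete follow-up of discontinuers; with fewer of them followed, less observed time is discarded. On the 2.5.3 reading the curve is a legitimate on-IMP display, but it answers a different question from rescue by Week 26 and can lie above or below the count. Neither reading gives a curve and a percentage that describe the same quantity. The output is descriptive, so no error rate is touched and the reported percentage itself is unaffected. It is a minor correction worth making.

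**What to change.** In 2.4.4.4:
- State how the 26-week treatment period there relates to the definition in 2.5.3, so that the two agree.
- Count first rescue through Visit 19 (Day 182 if that date is missing), regardless of IMP status.
- Censor non-rescued patients at Visit 19 or Day 182, or at the end-of-study or last-contact date if earlier.
- Use the same window for the number (%).
- If an on-IMP curve is also wanted, label it as such.

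The cost is a few lines of SAP text and one derivation rule. The end-of-study and last-contact dates are already named in 2.4.4.4, and no new data are needed.
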